Each participant will then perform a walking gait and sit-to-stand task as a baseline, in the University of Idaho Biomechanics Laboratory. An eight-infrared camera optical system (Vicon Motion Systems Ltd., Oxford, UK) and forceplate (AMTI, Watertown, MA, USA) will be used to collect the kinematic and kinetics data during the tasks. In addition, an eight-channel wireless electromyography (EMG) system (Delays, Inc., Natick, MA, USA) will be used to collect muscle activity during the gait and sit-to-

stand tasks, and the active straight leg raise (ASLR) special test. The participants in the treatment group will receive a Mulligan Concept evaluation and treatment administered by a Certified Mulligan Practitioner. The placebo group will undergo only the Mulligan Concept evaluation. The same tasks and ASLR will be repeated. Outcome measures and physical examination will also be repeated.

The study will be conducted under a randomized triple blinded placebo trial design. Neither the participants, the treating clinician, biomechanist, nor researcher collecting outcome measures will know the group designation of the participants. Conducting the trial in this manner will ensure the lowest possibility that any observed effects of the intervention are due to confounding factors.

Statistical Analysis

Sample size calculations were conducted to determine the appropriate number of participants that must be included. A sample size of 17 participants per group is needed to detect differences between groups with 80% power, and an *a priori* alpha of 0.05. Accounting for a reasonable 5% drop out rate, the final recommended number of participants is 36 (18 participants per group).

Specific Aim #1: Determine if Mulligan Concept manual therapy produces immediate changes in pain and self-reported function in women with PPGP.

A series of independent samples t-tests will be used to determine if a difference exists between the mean scores of the intervention and placebo groups on the VAS, PSFS, ADQ, and PGQ.

Specific Aim #2: Determine whether treatment with the Mulligan Concept immediately restores or alters dysfunctional gait characteristics and pelvic girdle motor control in women experiencing PPGP.

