The timing and amplitude of lumbar and thoracic spine rotations, as well as muscle activity, will be recorded and compared using descriptive statistics. Between groups analysis will consist of descriptive statistics to compare differences in timing, amplitude, and EMG activity after intervention.

Specific Aim #3: Identify intake factors that predict treatment outcome.

Standard multiple regression and step-wise multiple regression will be used to predict treatment outcome from different factors of interest (e.g., number of pregnancies, week of gestation, initial ADQ score, etc.).

Project Timeline

Preparation for participant recruitment will begin July 15th, 2017. Participant recruitment will take place between December 2017 and March 2018. Data collection will take place over 5-6 days in late March 2018. Data Analysis will take place between April and May 2018. Abstract and manuscript development and preparation for publication and presentation will take place through December 2018.

Interim Milestones

The following interim milestones will be used to hold the PI and research team accountable. These milestones will be shared with the research team and overseen by the PI. When appropriate and if a milestone is not met in a timely fashion, guidance will be sought from the Mentor and a plan for re-establishing the project timeline will be established and implemented.

Phase	Milestone	Timeline
Study Start Up	
 • IRB Approval • Award Announcement • Preparation • Pre-recruitment planning (e.g., creation of media material) 	
 • Prior to March 1, 2017 • May 31, 2017 • July 15- October 1, 2017 • October 1- December 1, 2017
Study Conduct	
 • Ready to Recruit • Materials completely distributed • 50% Enrollment Achieved • 100% Enrollment Achieved • Data Collection 	
 • December 1, 2017 • January 15, 2018 • February 20, 2018 • March 15, 2018 • Late March, 2018
Study Close-out	
 • Attendance at Annual Meeting • Publication within 12 months of study close 	
 • May, 2018 • December, 2018

Plans for developing and submitting future grant applications

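### Aim 2 asks whether treatment alters gait and motor control, but the planned between-group analysis is descriptive, with no interval estimate and no specified use of baseline

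*Combined protocol and SAP*

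**What the plan says.** All references are to the combined protocol and SAP.

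- **Objective (Statistical Analysis, Specific Aim #2):** the aim is worded as "Determine whether treatment with the Mulligan Concept immediately restores or alters dysfunctional gait characteristics and pelvic girdle motor control in women experiencing PPGP".
- **Method (same section):** timing and amplitude of lumbar and thoracic rotation, "as well as muscle activity, will be recorded and compared using descriptive statistics". The next sentence covers the group comparison: "Between groups analysis will consist of descriptive statistics to compare differences in timing, amplitude, and EMG activity after intervention".
- **Data available (Approach):** "Each participant will then perform a walking gait and sit-to-stand task as a baseline", with EMG recorded during both tasks and during the active straight leg raise. After the intervention, "The same tasks and ASLR will be repeated".
- **Contrast with Specific Aim #1:** "A series of independent samples t-tests will be used to determine if a difference exists between the mean scores" of the two groups, for four patient-reported scales only.
- **Specific Aim #3:** regression for a treatment outcome that is not defined and is not said to include biomechanical measures.

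The document gives no confidence interval, model, lead biomechanical variable or criterion for calling gait restored or altered.

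**The concern.** Aim 2 is worded as a question about a treatment effect. Its method is a stated choice, not a silence: the between-group analysis is to be descriptive. Aim 1, framed the same way, has inferential tests; Aim 2 has none.

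A side-by-side display of group summaries in a small trial will often show differences that look meaningful when the treatment does nothing. Without an interval, the plan gives no means of telling the two situations apart. It also leaves each woman's own baseline out of the specified group comparison, although that value is collected and could sharpen it.

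At stake is what the biomechanical half of the study can conclude. The Innovation section gives, as a reason for the study, that intervention trials have not yet examined whether these dysfunctions can be changed. That is the Aim 2 question.

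**Working it through.** **Inputs**

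- Group size: 10 per group, from the 20 women to be recruited (Approach), assuming an equal split; or 17 per group (Statistical Analysis). The document gives both totals, so both are carried through.
- Four rotation measures: lumbar and thoracic, each with timing and amplitude (Specific Aim #2). EMG measures are not counted, because the plan does not list them.
- Assumptions, not in the document: a 0.5 SD gap as an illustrative threshold; pairwise correlation between measures of 0 or 0.5 to 0.9; pre-post correlation of 0.5 to 0.9; normally distributed measures.

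**The plan's own figure**

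The plan gives no figure for Aim 2. Its general statement is "A sample size of 17 participants per group is needed to detect differences between groups with 80% power". The dropout step reproduces: 17/0.95 = 17.9, so 18 per group and 36 in total. The 17 itself cannot be reproduced, because no endpoint, effect size or SD is stated. Solved backwards for a two-sided two-sample t-test, it corresponds to a standardised difference of about 0.99. None of this is tied to a biomechanical measure.

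**Step 1: chance gap on one measure, no true effect**

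Standard error of the difference in means = sqrt(2/n) SD.

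- n = 10: sqrt(0.2) = 0.447; 0.5/0.447 = 1.118; two-sided probability 0.264.
- n = 17: sqrt(2/17) = 0.343; 0.5/0.343 = 1.458; two-sided probability 0.145.

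**Step 2: at least one such gap among four measures**

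If independent, 1 − (1 − p)^4:

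- n = 10: 1 − 0.736^4 = 0.706.
- n = 17: 1 − 0.855^4 = 0.465.

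Lumbar and thoracic rotation in the same gait are unlikely to be independent. With equal pairwise correlation r, the four standardised gaps share a common normal component. The probability is then one minus the integral, over that component, of the conditional probability that all four stay below the threshold.

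| Correlation between measures | 10 per group | 17 per group |
|---|---|---|
| 0 | 71% | 47% |
| 0.5 | 63% | 39% |
| 0.8 | 49% | 29% |
| 0.9 | 42% | 25% |

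**Step 3: the precision an interval would show**

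Unadjusted 95% half-width = t(0.975, 2n − 2) × sqrt(2/n):

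- n = 10: 2.101 × 0.447 = 0.94 SD.
- n = 17: 2.037 × 0.343 = 0.70 SD.

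ANCOVA half-width = t(0.975, 2n − 3) × sqrt(2/n) × sqrt(1 − ρ²), where ρ is the pre-post correlation:

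| ρ (assumed) | 10 per group | 17 per group |
|---|---|---|
| 0.5 | 0.82 SD | 0.61 SD |
| 0.7 | 0.67 SD | 0.50 SD |
| 0.9 | 0.41 SD | 0.30 SD |

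A 0.5 SD gap therefore lies well inside the unadjusted interval at either group size. Using the baseline already collected narrows the interval by roughly 13% at ρ = 0.5 (0.82/0.94 = 0.87) and 56% at ρ = 0.9 (0.41/0.94 = 0.44).

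**The case against.** The case on the other side has several parts.

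- **Exploratory status.** The section on future grant applications calls the trial exploratory and its data preliminary, and the Approach applies the word primary to patient-reported measures only. Descriptive reporting of biomechanics is a recognised choice in such a study. This stands as a limit on how strongly Aim 2 results may be claimed. It does not excuse giving no measure of uncertainty while the aim is worded as a determination.
- **Baseline may be used.** A reader might infer that only post-intervention values will be examined and baseline ignored. The text does not support that. The first Aim 2 analysis sentence does not say what is compared and could cover a descriptive pre-post summary, and differences after intervention could mean change. What holds is narrower: no change-score or baseline-adjusted comparison between groups is specified.
- **Randomisation.** A reader might infer that results would be confounded by existing differences. Under the stated randomised design, baseline differences would be chance ones, and adjustment mainly adds precision. That precision matters at these group sizes.
- **SDs allow an interval to be derived.** If means, SDs and group sizes are reported, a reader can compute the unadjusted interval. The plan does not commit to reporting them, and the adjusted interval could not be obtained that way.
- **Later research.** A reader might infer that this trial's gait results will decide whether future studies stop examining mechanisms. The passage is conditional, follows a proposal for a larger multi-site trial, and sets no decision rule. The point does not rest on it.
- **Magnitude.** The 0.5 SD threshold and the count of four measures are illustrative, and independence is the worst case shown. Hence the ranges.

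**Conclusion.** The mismatch between aim and method is real and worth correcting. A question about whether treatment changes gait is paired with a group comparison that carries no statement of uncertainty and specifies no use of the baseline.

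With no true effect, a 0.5 SD gap on a single measure is expected in about one trial in four at 10 per group and one in seven at 17. Across four measures the chance of at least one ranges from 42% to 71% and from 25% to 47%, depending on how correlated the measures are. These figures assume equal groups and normal data. Correlated measures reduce the problem but do not remove it.

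A reader might conclude that descriptive analysis is wrong in itself here. It is not: it would be acceptable if the aim were worded to match.

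**What to change.** Replace the between-group sentence under Specific Aim #2 with the following plan.

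1. List the measures: lumbar and thoracic rotation timing and amplitude, and a short named set of EMG measures.
2. For each, report the between-group difference with a 95% CI from ANCOVA of the post-intervention value on the same woman's baseline value.
3. Name one gait measure as the lead Aim 2 measure and label the rest exploratory. Do not add an uncorrected significance test for every measure: four independent tests at 0.05 would give a family-wise error of 1 − 0.95^4 = 19%.
4. Limit the conclusion to whether treatment alters gait or motor control. ANCOVA cannot show that gait is restored unless the plan defines restoration against a stated reference.

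Alternatively, keep the descriptive analysis, reword Aim 2 to describe gait and motor control in the two groups, and make no claim that either is restored or altered.

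The cost is a change of wording and a few model fits on data already planned. No extra participants, visits or measurements are needed. The downside is that the intervals will be visibly wide and the Aim 2 claims more modest.

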Twenty pregnant volunteers, ages 20-45 years, will be recruited for the study. Participants will be between their 20th-34th week of gestation, with reported pregnancy-related lumbopelvic pain. Participants would be excluded for any of the following criteria:

- orthopaedic or neurological problems with walking (other than PPGP)
- prior surgery of the lumbar spine, pelvis, hip, or knee
- fracture
- known malignancy
- active inflammation in the lumbar spine or pelvis
- ankylosing spondylitis, Scheuermann's kyphosis, active polyarthritis, or severe osteoporosis
- any pulmonary, cardiac, visual, auditory, or cognitive disorders
- any other multi/co-morbidities that limit the volunteers ability to complete a gait and sit-to-stand task

Volunteers will be recruited from Latah County, Idaho and surrounding areas by word of mouth and print and social media. Pregnant women who express interest in the study will be given an informational packet explaining the methods, risks, and benefits of participation. If the women decide to participate they would sign a consent statement and conduct an initial questionnaire, sent via online link. The survey would be used to determine inclusion and exclusion criteria, and group assignment (i.e., intervention group, placebo group). Un-paired t-tests will be conducted to determine whether significant differences exist between intervention and control groups in age, weight, height, as well as gestational week and number of pregnancies. Randomly stratifying the participants in to groups in this manner minimizes the potential confounding variables.

Participants will report to the University of Idaho Integrated Sport Medicine and Rehabilitative Therapy Clinic for initial patient reported outcome measures collection and standardized examination. Primary patient reported outcome measures include the Visual Analog Pain Scale, the Pelvic Girdle Questionnaire, the Assessment of Disablement Questionnaire, the Patient Specific Function Scale, and the Short Stress State Questionnaire. The examination will include history, palpation, special tests (e.g., Posterior Pelvic Pain Provocation test, Active Straight Leg Raise), and neurological screen.

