This grant application marks continued steps toward becoming an independent and successful researcher. The project will enable the PI to further establish her work in patient-care and manual therapy research, where she has had previous experience in relation to core motor control. Additionally, this project will aid in the PI's professional development by establishing University and community collaborations.

Information gathered from this exploratory trial will greatly inform next steps in a long line of research and allows the PI to collect preliminary data and develop evidence for interventions in an underserved population. For example, if the central hypothesis is confirmed, further investigation into the Mulligan Concept as treatment for PPGP in this population is warranted. A larger-scale multi-site randomized control trial with large sample size and more diverse sample would be the next logical step to create more robust evidence of the technique. Once the efficacy of the treatment protocol is established, exploration of a patient-applied treatment as a home program would be developed. If the kinematic, kinetic, pain and dysfunction effects can be well established, continued research would not necessarily focus on the biomechanical mechanisms, but would be more clinical in nature; a full scale clinical trial, focusing on treatment outcome, comorbidity, predictive factors of treatment outcome, risks, and side effects, etc. Future research will not be equipment heavy, but need funding primarily for participant recruitment, clinician training, and researcher salaries. Exploratory/Developmental research grants such as the NIH R21, or multi-site collaborative grants such as the CTR-IN Multi-Site Research Project Program, would be an ideal funding mechanisms for the next stages of this research line.

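### Aim 3 plans step-wise selection from an open factor list for an outcome it does not name; one pre-specified model that reports every factor would be better at no data cost.

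*Combined protocol and SAP*

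**What the plan says.** The objective of Specific Aim #3 is "Identify intake factors that predict treatment outcome". Its analysis is one sentence: "Standard multiple regression and step-wise multiple regression will be used to predict treatment outcome from different factors of interest", with the factors given as "e.g., number of pregnancies, week of gestation, initial ADQ score, etc".

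The rest of the combined protocol and SAP does not complete that sentence:

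- **Outcome.** The Approach section says "Primary patient reported outcome measures include the Visual Analog Pain Scale, the Pelvic Girdle Questionnaire, the Assessment of Disablement Questionnaire" and adds two more, so five measures are all primary. Aim 1 compares "the mean scores of the intervention and placebo groups on the VAS, PSFS, ADQ, and PGQ", which is four of the five. Aim 3 names none of them.
- **Factors.** The list is open. No entry or removal rule for step-wise selection is given.
- **Population and model terms.** The plan does not say whether both groups or only treated women are modelled. It states no group term and no group-by-factor term.
- **Size.** The Approach section gives "Twenty pregnant volunteers". The sample size paragraph says "the final recommended number of participants is 36 (18 participants per group".
- **Status.** The section on future grant applications says "Information gathered from this exploratory trial will greatly inform next steps in a long line of research" and lists predictive factors among the topics of a later full-scale trial.

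**The concern.** When the data choose the factors, from a list that can grow during analysis and for an outcome that can be settled afterwards, the number of chances to find something is unknown. Step-wise selection then presents only what passed. In a sample of 20 or 36, any factor that passes must show a sizeable R-squared, so a chance result looks convincing.

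There is a separate question of meaning. A model without a group-by-factor term relates intake factors to the later score. It can describe prognosis, but it cannot separate women who would have had a good score anyway from women whom the treatment helped.

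At stake is what is carried into the next study. A chance factor, or a purely prognostic one, could be reported as predicting response to the Mulligan treatment.

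**Working it through.** **Inputs from the document.** Three named factors; alpha 0.05 (sample size paragraph, the only alpha stated); N=20 (Approach) or N=36 (Statistical Analysis). Aim 3 has no figure of its own to reproduce. The 36 follows from the plan's own dropout step: 17/0.95 = 17.9, so 18 per group and 36 in all. The 20 does not fit this, so both sizes are carried.

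**Assumptions.** Entry at p<0.05 and removal at p>0.10; independent candidate factors; 5 or 8 candidates as examples of a longer list.

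**1. Chance of keeping at least one noise factor.** For k independent null factors this is about 1 - 0.95^k. The simulation used forward step-wise with removal, 4,000 runs per cell, standard error 0.006-0.008.

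| Candidates k | 1 - 0.95^k | Simulated, N=20 | Simulated, N=36 |
|---|---|---|---|
| 3 (named) | 0.143 | 0.148 | 0.149 |
| 5 (assumed) | 0.226 | 0.223 | 0.220 |
| 8 (assumed) | 0.337 | 0.339 | 0.327 |

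The rate depends on k and the entry rule, hardly at all on N.

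**2. If initial ADQ is truly prognostic.** Two noise candidates remain: 1 - 0.95^2 = 0.098. Simulation with a baseline-to-post correlation of 0.5-0.7 gives 0.102-0.106 at N=20 and 0.098-0.106 at N=36, so about 10%.

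**3. The standard model with the same three factors.** At least one coefficient has p<0.05 in 0.137 (N=20) and 0.141 (N=36) of 8,000 null runs, and in 0.122-0.128 if only 10 or 18 women are modelled. The overall F-test rejects in 0.046-0.053. So at three factors step-wise (about 14%) is barely worse than reading coefficients singly (12-14%).

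**4. Apparent fit of a factor that passes.** The smallest R-squared reaching p<0.05 is t²/(t² + N - 2), with t the two-sided 5% point on N - 2 df.

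- N=20: t = 2.101, t² = 4.41, 4.41/(4.41 + 18) = 0.197.
- N=36: t = 2.032, t² = 4.13, 4.13/(4.13 + 34) = 0.108.

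The mean R-squared of one noise factor, given that it passes, comes from Beta(1/2, (N-2)/2): 0.269 at N=20 and 0.152 at N=36.

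**5. Prognosis or benefit.** Simulated with 1:1 allocation, standardised factor and residual SD 1; slopes are assumed.

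- A factor with slope 0.5 that modifies nothing is flagged by the model without interaction in 52% (N=20) or 78% (N=36) of runs. These are correct prognostic detections.
- A factor that only modifies the treatment effect (slope difference 0.5 to 1.0) is flagged by that model in 5-7% of runs, close to chance.

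**6. What an interaction term would give.** In a model with group, baseline score, one factor and its interaction, the mean 95% CI half-width is about 1.1 residual SD per SD of the factor at N=20 and 0.74 at N=36. Power for slope differences of 0.5 and 0.8 is about 16% and 30% at N=20, and 28% and 57% at N=36. With three null factors examined this way, at least one interaction CI excludes zero in about 14% (N=20) or 13% (N=36).

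**The case against.** **Step-wise adds little.** Standard regression is planned beside it, and at three factors the two have nearly the same chance-finding rate. This stands. A reader might infer that step-wise is by itself the main source of false factors; the figures for the named factors do not support that. The 23% and 34% rest on candidate counts that the document does not give. What remains is that the list has no stated end, and that step-wise reports only the survivors.

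**Who benefits is not the stated aim.** Aim 3 speaks of predicting outcome. It does not mention moderators, responders or patient selection. A reader might infer that the plan sets out to find responders and wrongly omits an interaction. The document does not support this: prognosis is a fair reading, and silence about an interaction does not exclude one. What stands is that the plan should say which is meant, because without an interaction only prognosis can be claimed.

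**Interaction models have costs.** A separate model for each factor would lose the mutual adjustment that the planned standard regression gives, and the intervals would be wide. This also stands, and is why the fix keeps one joint model and makes interactions conditional on intent.

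**It is exploratory.** True, and it lowers the weight of the point. It does not supply an outcome or a factor list.

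**Conclusion.** The point holds as a cheap improvement in method, with limited harm. Data-driven selection from an open list, for an unnamed outcome, at N=20 or 36, is a weaker choice than one pre-specified model that reports every factor.

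Only the figures of about 14% (all three named factors noise) and about 10% (initial ADQ prognostic) are tied to factors in the document, and even these assume entry at p<0.05. The higher rates illustrate what an open list permits. The apparent R-squared figures depend on N, on which the Approach and Statistical Analysis sections conflict and must be reconciled.

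The missing interaction is a limit on interpretation and not a demonstrated error. Nor does the document support an inference that chance factors would pass straight into practice: predictive factors are left for study in a later trial.

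**What to change.** In Specific Aim #3:

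1. Delete step-wise selection.
2. Before analysis, name one outcome from the four Aim 1 measures and a short closed list of intake factors. Which outcome and which factors are for the investigator.
3. Fit one standard multiple regression on all randomised participants: post score on group, baseline score and all listed factors. If ADQ is the outcome, initial ADQ is the baseline score and enters once.
4. Report every coefficient with its 95% CI as exploratory, together with the overall F-test. Group and baseline score contribute to that test, so it does not by itself show that a listed factor matters.
5. Label the results as prognostic.
6. Only if effect modification is intended, add group-by-factor terms, reported as estimates with 95% CIs and no significance claim.

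**Cost.** Wording only. The outcome measures are already collected before and after, and the other two named factors are already recorded for the baseline comparison. Fewer factors are examined. With three factors besides the baseline score the model has 6 coefficients (intercept, group, baseline, three factors), leaving 20 - 6 = 14 or 36 - 6 = 30 residual df. Three interactions bring this to 11 or 27. Interactions stay imprecise: the half-widths of about 1.1 and 0.74 residual SD are for one interaction at a time, and fitting several together would not narrow them. The chance of about 13-14% that at least one of three null interaction CIs excludes zero should be stated with the results.

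### Aim 3 offers the initial ADQ score as a predictor of an undefined treatment outcome; if that outcome is ADQ change, an association is built in even with no treatment effect

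*Combined protocol and SAP*

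**What the plan says.** The aim is stated as "Specific Aim #3: Identify intake factors that predict treatment outcome". The method is one sentence: "Standard multiple regression and step-wise multiple regression will be used to predict treatment outcome", using "factors of interest (e.g., number of pregnancies, week of gestation, initial ADQ score, etc". Nothing under Aim 3 names the outcome scale, chooses between post score and change, says which arms enter the model, or includes a term for arm.

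ADQ is also an outcome. The Approach section's list of primary patient-reported measures includes "the Assessment of Disablement Questionnaire, the Patient Specific Function Scale, and the Short Stress State Questionnaire", and Aim 1 tests whether "a difference exists between the mean scores of the intervention and placebo groups on the VAS, PSFS, ADQ, and PGQ". The questionnaires are completed before the intervention, and afterwards "Outcome measures and physical examination will also be repeated". Aim 1 concerns immediate effects ("Determine if Mulligan Concept manual therapy produces immediate changes in pain and self-reported function in women with PPGP") and no later visit is described, so the repeat appears to fall in the same visit.

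**The concern.** The candidate list treats the starting value of an outcome scale like an obstetric characteristic and lets regression decide whether it predicts outcome. If the outcome is ADQ change (post minus initial), the initial score sits on both sides of the equation. Measurement error and regression to the mean then produce a negative association whether or not treatment does anything. The report could say that women with worse initial disability respond better when the data show only this coupling.

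The section on future grant applications says that the trial's results will shape later work, and it names predictors of treatment outcome as one topic. A built-in association could be carried into that work as a finding.

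**Working it through.** **The plan's own figures.** The documents give no number for Aim 3. The sample size arithmetic does reproduce: 17 / (1 - 0.05) = 17.9, rounded up to 18 per group, 36 in total, or 2 x 17 = 34 completers. The Approach section instead plans 20 women. Both sizes are therefore used, with treated-only samples of 10 (half of 20) and 17, because Aim 3 does not say which arms are analysed.

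**Assumptions not in the documents.** Pre-post correlation rho from 0.5 to 0.9, equal pre and post variances, normal scores, no treatment effect, two-sided alpha 0.05 (the plan gives 0.05 without sidedness).

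**Outcome is ADQ change.** Let X be the initial and Y the post score, each with variance s².
- cov(X, Y - X) = rho·s² - s² = -(1 - rho)·s²
- var(Y - X) = 2(1 - rho)·s²
- corr(X, Y - X) = -(1 - rho) / sqrt(2(1 - rho)) = -sqrt((1 - rho)/2)

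For example, at rho = 0.7 this is -sqrt(0.15) = -0.39. Treatment does not appear in the formula. Simulation with initial ADQ as the only predictor gives these shares of no-effect trials in which it is significant, to within about one percentage point:

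| rho | built-in r | n=20 | n=34 | treated only, n=10 | treated only, n=17 |
|---|---|---|---|---|---|
| 0.5 | -0.50 | 64% | 88% | 33% | 56% |
| 0.7 | -0.39 | 41% | 64% | 19% | 35% |
| 0.8 | -0.32 | 28% | 45% | 14% | 24% |
| 0.9 | -0.22 | 16% | 25% | 9% | 14% |

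Adding two unrelated covariates changes little: 59%, 36%, 25% and 15% at 20 women. The unrelated covariates themselves stay near 5%, so this is not chance selection. Adding an arm main effect does not remove it (14% to 57% at 20 women).

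**Outcome is ADQ post score.** Here corr(X, Y) = rho. A significant coefficient, however frequent, detects a correlation that really exists, so it is not a false positive. It carries no information on whether treatment worked better in some women. The arm-by-initial-ADQ interaction does address that, and under no treatment effect it rejects at close to 5%: 4.5% to 5.3% with 20 women and 5.0% to 5.2% with 36, for either outcome form.

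**How the two forms relate.** With X in the model, regressing Y - X rather than Y lowers the coefficient of X by exactly 1 and leaves every other coefficient unchanged. The choice of form matters only for how the initial score's own coefficient is read, provided that the score is kept in the model.

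**Outcome is another questionnaire.** With an assumed cross-scale correlation of 0.6 and 20 women, initial ADQ is significant against change on that scale in 23% down to 8% of trials. Forcing in that scale's own initial score brings this to about 5% if ADQ adds nothing beyond it. If instead the 0.6 correlation between scales holds undiminished from before to after (rho 0.7 to 0.9), initial ADQ remains significant in about 26% down to 11% of trials with 20 women and 44% down to 16% with 34.

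**The case against.** A reader might infer that initial ADQ will often be falsely found to predict treatment outcome whatever the outcome is. The documents do not support that, for four reasons.

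- **The outcome is undefined.** Reading it as one of the questionnaires is reasonable, since the protocol uses outcome measures as its term for them, but it remains an inference. Aim 2 also has kinematic and EMG outcomes, which would not carry this coupling.
- **The post-score branch is real prognosis.** Aim 1 compares "mean scores of the intervention and placebo groups on the VAS, PSFS, ADQ, and PGQ" and mentions no change score, so a post score is at least as likely. Initial disability then truly predicts later disability, and that is a correct, if unsurprising, answer to the aim as worded. What remains is the risk of reading it as response to treatment. That is the missing interaction, and it applies equally to gestational week or any other main effect.
- **The size depends on rho.** A repeat within one visit may have a high rho, which weakens the change-score coupling, and treated-only samples weaken it further. At the low end the rate is 9%, not far above nominal.
- **The stakes are limited.** The trial is described as exploratory, the predictor list is illustrative, and no stated decision rests on this coefficient. With a post-score outcome, a standard regression that includes initial ADQ is already the adjusted model, so part of the remedy is labelling.

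All four stand, and they limit the point. They do not remove it: the plan permits the change-score analysis, and in that analysis the association is an artefact at every rho tried.

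**Conclusion.** The concern holds in a limited form. Aim 3 allows the initial value of an outcome scale to be selected as a predictor of change on that same scale. With no treatment effect, that would be declared significant in about 64% down to 16% of trials with 20 women and 88% down to 25% with 34, or 33% down to 9% and 56% down to 14% with 10 or 17 treated women only, against a nominal 5%. These rates rest on rho of 0.5 to 0.9 and equal variances, neither given in the documents, and on ADQ change being the outcome. For a post-score outcome there is no false positive, only a prognostic association that must not be described as response to the Mulligan Concept. Severity is modest because the aim is exploratory. Confidence is moderate because the outcome definition and rho are both assumed.

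**What to change.** State in Aim 3 that:
1. the outcome is the post-session score of a named scale;
2. that scale's own initial score is forced into every model as an adjustment covariate, outside step-wise selection, and its coefficient is not reported as a predictor of treatment response;
3. initial ADQ is removed from the candidate list when ADQ is the outcome;
4. any remaining main-effect association, including initial ADQ with another scale, is described as prognostic only;
5. any claim about response to treatment rests on an arm-by-factor interaction in a model that includes both arms.

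Item 4 is needed because, as the last calculation shows, adjusting for a scale's own baseline does not always remove an association with initial ADQ. The cost is a few sentences and one degree of freedom per model, with no new data. An interaction, where wanted, also needs the arm and product terms, and its estimate will be imprecise with 20 to 36 women.
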